Power calculation: A cluster randomized trial (CRT) will be conducted at 12 schools that provide symptomatic SARS-CoV-2 testing to students and staff. Schools will be randomized 1:1 to either screening testing plus symptomatic testing, or symptomatic testing only. All participants including students and staff will receive the same assignment within a given school. The primary outcome is transmission rate, defined as the ratio of the number of contacts testing positive for SARS-CoV-2 to total number of contacts for each school-based case. We hypothesize that schools performing screening testing will have lower transmission rates than routine symptomatic testing. We expect that transmission rates with screening testing or routine symptomatic testing will be 2% and 8%, respectively. With the assumptions that the intracluster correlation coefficient (ICC) is 0.02 and the standard deviation of transmission rate is 0.22, 6 schools in each arm with an average of 117 participants per school will achieve 80% power to detect a difference in transmission rates between the two study arms using a two-sided t-test at a significance level of 0.05 (Table 3). PASS 15.0 was used to conduct this power analysis.

Table 3. Sample Size

| ICC | Standard deviation | # of participant per school |
|------|--------------------|-----------------------------|
| 0.01 | 0.25 | 83 |
| | 0.30 | 188 |
| | 0.33 | 376 |
| | 0.35 | 803 |
| 0.02 | 0.22 | 117 |
| | 0.23 | 164 |
| | 0.24 | 252 |
| | 0.25 | 486 |
| 0.03 | 0.20 | 221 |
| | 0.21 | 806 |

Analysis plan: The generalized estimating equation (GEE) model with appropriate link function (e.g., identity for primary outcome) will be used to analyze the CRT data, in which the correlation among participants within each school needs to be considered. The autoregressive of first order as a working correlation structure will be used, and participants with missing values will be excluded from the GEE analysis. The GEE model includes the group indicator and other potential factors, including: race/ethnicity, insurance status, age, gender, underlying diagnoses, masking, distancing, ventilation, location of transmission. Least square means for the primary outcome per group will be estimated, and the standard errors will be calculated with the GEE sandwich method when accounting for within-school correlation. All analyses will be conducted using SAS (SAS Institute, Cary, NC) at the two-sided significance level of 0.05.

Data Management.

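### The 80% power for 6 schools per arm ignores that only 12 units are randomised; with the 10 degrees of freedom they support, the same inputs give about 72%

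*Combined protocol and SAP*

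**What the plan says.** The only power justification is the first paragraph of Section E (Statistical Plan), with Table 3.

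- Size: "A cluster randomized trial (CRT) will be conducted at 12 schools".
- Allocation: "Schools will be randomized 1:1 to either screening testing plus symptomatic testing, or symptomatic testing only". Everyone in a school receives that school's assignment.
- Effect: "We expect that transmission rates with screening testing or routine symptomatic testing will be 2% and 8%, respectively".
- Clustering: "intracluster correlation coefficient (ICC) is 0.02".
- Spread of the outcome: "the standard deviation of transmission rate is 0.22".
- Claim: "6 schools in each arm with an average of 117 participants per school will achieve 80% power".
- Test on which the claim rests: "two-sided t-test at a significance level of 0.05".

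Table 3 gives the participants per school for ten ICC and SD combinations. The software is named as PASS 15.0, but the degrees of freedom are not stated. The analysis paragraph that follows specifies a GEE with sandwich standard errors; it gives no small-sample correction and no reference degrees of freedom.

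**The concern.** The ICC enters the calculation through the variance, as it should. The second cost of randomising few clusters is that the between-arm variance is estimated from only 12 schools, which calls for a t reference with 10 degrees of freedom. An ICC of 0.02 and a 117-per-school requirement that fits a critical value of 1.96 suggest that this cost was left out.

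If so, the trial as described in Section E has less power than it claims. The chance of missing the assumed effect would be about 28%, not 20%. A non-significant result could then be over-read as evidence that screening testing adds nothing, which is the question the study is meant to answer. Table 3 would also suggest that larger schools can offset a higher ICC or SD in cases where, with 12 schools, they cannot.

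**Working it through.** **Inputs (all from Section E).** Difference d = 0.08 − 0.02 = 0.06; SD σ = 0.22; ICC ρ = 0.02; k = 6 schools per arm; m = 117 per school; two-sided α = 0.05.

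**Standard error and noncentrality.**

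- Design effect = 1 + (m − 1)ρ = 1 + 116 × 0.02 = 3.32
- Participants per arm = 6 × 117 = 702; effective number = 702 / 3.32 = 211.4
- SE = σ√(2 × 3.32 / 702) = 0.0214
- Noncentrality = 0.06 / SE = 2.804

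**Power under three references.**

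| Reference | Degrees of freedom | Power |
|---|---|---|
| Normal | – | 80.1% |
| t, participants counted | 2(702 − 1) = 1,402 | 80.0% |
| t, schools counted | 2(6 − 1) = 10 | 71.5% |

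The plan's figure is therefore reproduced, and 117 is exactly the smallest school size that reaches 80% under either of the first two references. With 10 degrees of freedom the critical value rises from 1.96 to 2.23 and power falls by about 8.5 points.

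**Detectable difference.** With 10 df, 80% power needs a noncentrality of 3.11, so the detectable difference is 3.11 × 0.0214 = 0.0665, or 6.65 points.

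**Table 3, row by row (12 schools).** The limiting power lets m grow without bound, so that the noncentrality tends to d / (σ√(2ρ/6)).

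| ICC | SD | Stated m | Power, normal | Power, 10 df | m for 80%, 10 df | Limiting power, 10 df |
|---|---|---|---|---|---|---|
| 0.01 | 0.25 | 83 | 80.2% | 71.6% | 126 | 96% |
| 0.01 | 0.30 | 188 | 80.1% | 71.5% | 412 | 88% |
| 0.01 | 0.33 | 376 | 80.0% | 71.5% | about 3,900 | 81% |
| 0.01 | 0.35 | 803 | 80.0% | 71.4% | none | 76% |
| 0.02 | 0.22 | 117 | 80.1% | 71.5% | 320 | 85% |
| 0.02 | 0.23 | 164 | 80.1% | 71.5% | 885 | 82% |
| 0.02 | 0.24 | 252 | 80.0% | 71.4% | none | 79% |
| 0.02 | 0.25 | 486 | 80.0% | 71.4% | none | 75% |
| 0.03 | 0.20 | 221 | 80.0% | 71.5% | none | 77% |
| 0.03 | 0.21 | 806 | 80.0% | 71.4% | none | 73% |

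The stated sizes agree with a normal or participant-level reference to within 0 to 6 participants in every row, so the omission runs through the whole table.

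**Sixteen schools.** With k = 8 and m = 117, SE = 0.0185 and the noncentrality is 3.238. Power is 85.3% with 14 df (89.9% if participants are counted). The detectable difference at 80% power is 3.013 × 0.0185 = 0.056, or 5.6 points.

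**The case against.** **The degrees of freedom are not stated.** True. The reference used is inferred from the match, and a normal approximation fits Table 3 slightly better than participant-level df: for the last row the plan has 806, the normal gives 808 and participant-level df gives 812. Neither reflects 12 schools, so the correction is the same.

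**The trial may have sixteen schools.** The Study Setting and Populations text in Section C says sixteen will take part, and the Screening Testing text in D1 says eight of them will be randomised to screening. Section A, the milestones table and Section E say twelve. With sixteen schools and 14 df, the main scenario and every Table 3 row at its listed size have about 85% power, and there is no shortfall against 80%. This stands as a limit on the practical consequence. It does not rescue the published figures, which are given for 6 schools per arm.

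**The planned analysis is a GEE, not a t-test on schools.** Also true, and 71.5% applies to a test that uses a 10-df critical value. But the power claim itself names a t-test. With 12 clusters, uncorrected sandwich errors tend to be too small, so a large-sample reference could approach 80% only by exceeding the nominal 0.05 level.

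**The inputs are themselves uncertain.** The outcome is defined per school-based case while the calculation counts participants, and 117 is an average although the formula assumes equal schools. Both points apply to the 80% as much as to the 72%. The corrected figures are therefore conditional on the plan's own inputs.

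**Conclusion.** The concern holds. For the design in Section E, power is 71.5%, not 80%, and the plan's figure arises only when the small number of randomised schools is left out of the reference distribution. The result takes the plan's effect, SD, ICC and school size as given, assumes equal school sizes, and uses a two-sided 5% test with school-level degrees of freedom. If sixteen schools is the operative design, the claim of at least 80% is met for the stated inputs, but the text and Table 3 would still need to be rewritten for it.

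**What to change.** 1. Reconcile the number of schools across Sections A, C, D1 and E.
2. Restate power with school-level degrees of freedom and say so in the text: 72% for 12 schools of 117 (detectable difference 6.7 points), or 85% for 16 schools of 117 (5.6 points).
3. Recompute Table 3 on the same basis. If the design is 12 schools, mark the five rows that cannot reach 80% at any school size (ICC/SD 0.01/0.35, 0.02/0.24, 0.02/0.25, 0.03/0.20 and 0.03/0.21), and note that 0.01/0.33 would need about 3,900 per school.
4. State in the analysis paragraph the reference degrees of freedom and the small-sample correction to be used with the GEE sandwich errors, so that the test matches the one that was powered.

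The cost is a revised power statement, a recomputed table and one added sentence. No extra schools or participants are needed.

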School-based transmission will be determined by two methods. First, all close contacts of an infectious case in the school, identified through contact tracing by school staff and administrators, will be approached to participate in the study (as described above). Those electing to participate will undergo a contact interview (Appendix 2) to understand their behaviors and potential other COVID-19 exposures. Furthermore, the school contact tracer will complete a survey on the relationship of the case to each contact that provides information on the location of the exposure (e.g., classroom, lunch, extracurricular activity), distance between case and contact, use of barriers, masking adherence, and total amount of time the contact was exposed to the case (Appendix 3). The contacts will be offered testing 5-7 days after a school exposure. All contacts testing positive will undergo an independent review by five study team members using the information obtained from the case interview, contact interview, and contact tracing interview to determine whether a school-based transmission has occurred. These transmission events will be classified into the following categories with standardized definitions that were developed in conjunction with the CDC: probable, possible, unlikely, and unable to determine.

The second method to evaluate school-based transmission will be to collect weekly data from the schools, as participation in the above individual assessments is unlikely to reach 100%. The additional data to be collected will include total number of new staff and student cases, total number of new contacts, and number of school-based contacts that become new cases during their quarantine period. The secondary transmission rate will be calculated based on the number of positive school-based contacts per positive case. This method will provide the most conservative/greatest estimate of school-based transmission without knowledge of an individual's exposure to a potential household or community case.

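### The 80% power at 6 schools per arm needs all 117 participants per school in the model, with no allowance for the planned exclusion of anyone with a missing value

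*Combined protocol and SAP*

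**What the plan says.** The power calculation in Section E sets out a two-arm cluster trial in 12 schools: "Schools will be randomized 1:1 to either screening testing plus symptomatic testing, or symptomatic testing only". Its inputs are these:

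- Effect: "We expect that transmission rates with screening testing or routine symptomatic testing will be 2% and 8%, respectively".
- Variability: "the intracluster correlation coefficient (ICC) is 0.02 and the standard deviation of transmission rate is 0.22".
- Test: "using a two-sided t-test at a significance level of 0.05".
- Result: "6 schools in each arm with an average of 117 participants per school will achieve 80% power".

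Table 3 gives the participants needed per school for ten combinations of ICC and standard deviation. Neither the text nor the table states an expected rate of missing data, an inflation for it, or whether the entries count enrolled or analysed people.

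The analysis plan in the same section specifies a GEE with the arm and further potential factors: "race/ethnicity, insurance status, age, gender, underlying diagnoses, masking, distancing, ventilation, location of transmission". It then states that "participants with missing values will be excluded from the GEE analysis".

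Section D1 (Assessment of School-based Transmission) says of the contact interviews and related assessments that "participation in the above individual assessments is unlikely to reach 100" per cent, and for that reason adds weekly school-level counts as a second method.

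The number of schools differs between sections. Section A, Table 2 in Section C and Section E say 12. Section C (Study Setting and Populations) and Section D1 (Screening Testing) say 16, with 8 randomized to screening.

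**The concern.** A sample size that just reaches 80% has no room for loss, yet the analysis rule a few lines later creates loss. A person whose outcome is known would still leave the primary analysis if one of up to nine covariates were blank.

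Several covariates have sources that Section D1 makes optional. Insurance is asked in the data elements survey, which needs separate consent. Contact interviews cover only those who choose to take part. The school mitigation survey is described as something schools may complete.

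Two things are at stake. The first is precision: if 117 is an enrolment figure, the analysed number is smaller, and a null result would be read as better powered than it was. The second is selection. Screening participants give consent and demographic information before testing starts, whereas people in the other arm reach the surveys through symptomatic testing or contact tracing. Completeness could therefore differ by arm, and dropping incomplete records could then bias the comparison. The documents do not show that this will happen, but the rule exposes the trial to it without need.

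**Working it through.** **Inputs (all from Section E):** difference d = 0.08 − 0.02 = 0.06; SD = 0.22; ICC = 0.02; K = 6 schools per arm; m = 117 per school; two-sided alpha 0.05.

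**Formula:**

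- Design effect: DE = 1 + (m − 1) × ICC
- SE² = 2 × SD² × DE / (K × m)
- Power ≈ Φ(d/SE − 1.96)

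**Reproducing the stated figure:**

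- DE = 1 + 116 × 0.02 = 3.32
- SE² = 2 × 0.0484 × 3.32 / 702 = 0.000458, so SE = 0.0214
- d/SE = 2.804, so power = Φ(0.844) = 80.1%

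A t reference with participant-level degrees of freedom (2 × 6 × 117 − 2 = 1402) gives 80.0%. At m = 116 the normal formula gives 79.97%, so 117 is the smallest number that reaches 80%. The ten rows of Table 3 all come out at 80.0% to 80.2% with nobody excluded, so no row contains an allowance. (With between-school degrees of freedom, 2 × 6 − 2 = 10, the figure would be 71.5%. That does not match the plan's calculation. It is a separate matter and is not used here.)

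**Applying exclusions.** The documents give no rate, so a range is assumed. If 117 is the enrolled number, the analysed number is m = 117 × (1 − x):

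| Excluded (assumed) | Analysed per school | Power, 6 per arm | Power, 8 per arm |
|---|---|---|---|
| 0% | 117 | 80.1% | 89.9% |
| 10% | 105.3 | 78.8% | 89.0% |
| 20% | 93.6 | 77.2% | 87.8% |
| 30% | 81.9 | 75.2% | 86.2% |
| 50% | 58.5 | 69.3% | 81.2% |

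Worked line for 20% at 6 per arm: DE = 1 + 92.6 × 0.02 = 2.852; SE² = 0.0968 × 2.852 / 561.6 = 0.000492; d/SE = 2.706; power = Φ(0.746) = 77.2%.

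The loss is gradual because much of the variance is between schools: DE falls as m falls. At 6 per arm, power drops more than 2 points below 80% only once exclusions exceed about 15%. At 8 per arm, 55 analysable people per school suffice for 80%, so the target survives until about 53% are excluded.

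**Enrolment needed to keep 117 analysable,** 117/(1 − x): 130 at 10%, 147 at 20%, 168 at 30%, 234 at 50%.

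**How item-level gaps add up.** If each of nine factors were missing independently in 5% of people, 0.95⁹ = 63% would be complete (m = 73.7), with power 73.5% at 6 per arm. At 10% each, 0.90⁹ = 39% would be complete (m = 45.3), with power 63.9% at 6 per arm and about 76% at 8 per arm. Independence is an unfavourable assumption, because items from the same form tend to be missing together.

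**The case against.** The strongest reply is that nothing in the power calculation is miscalculated. The 80% and all of Table 3 reproduce, 117 may already mean analysed participants, and no section caps enrolment at 117. That stands. The gap is that the plan does not say which number it means.

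A reader might infer from the D1 sentence on incomplete participation that the protocol itself predicts missing values in the model. It does not. The sentence concerns contacts who decline the individual assessments, and it introduces the school-level data that are meant to compensate. Someone who never takes part does not reduce a count of participants. The sentence bears on the point only where a person's outcome is known but the interview was declined.

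A reader might also note that ventilation is not among the items described for any form in D1, and conclude that the rule leaves nobody in the model. The forms themselves are in appendices that are not available here, and the analysis plan calls the covariates potential factors, so an uncollected variable would presumably not be entered. This is something to check and no more.

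Nor do all the covariates depend on volunteers. The school contact tracer records masking adherence, distance and location of exposure, and demographics are captured at sample collection.

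Finally, the percentages in the table use an unadjusted two-mean formula with SD and ICC held fixed. The power of the adjusted GEE was not computed. That limits the figures to an indication of size.

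**Conclusion.** The point holds in a limited form. At 6 schools per arm the stated power has no reserve, and the same section prescribes an exclusion rule that could use up a reserve if there were one. If 117 is the enrolled number at 12 schools, the cost is about 1 point of power at 10% exclusion, 3 at 20%, 5 at 30% and 11 at 50%.

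It is tempting to go further and say that the trial as analysed lacks its stated power. The documents do not support that. They give no missing-data rate, they do not say whether 117 is enrolled or analysable, and with the 16 schools described in Sections C and D1 power starts at 89.9% and is still about 81% when half are excluded. The extra schools are not presented as an allowance for missing data, however, and the power statement and Table 3 rest on 12.

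What does not depend on resolving these uncertainties is that excluding people with a known outcome because a covariate is blank gives up precision and invites selection bias for no gain.

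**What to change.** 1. **Primary model.** Do not exclude participants from the primary GEE for missing covariates. Keep everyone with an observed outcome, using either an arm-only model or imputed baseline covariates. Report the complete-case adjusted model as a sensitivity analysis.
2. **Label the numbers.** State that 117 and every Table 3 entry are analysable participants per school.
3. **Restate power.** Reconcile 12 with 16 schools, then give power for that number and for an expected exclusion rate, with the basis for the rate. If any exclusions remain, give the matching enrolment target.
4. **Check the covariates.** Confirm that ventilation is recorded on a form before listing it in the model.

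The cost is a few sentences in the statistical plan and a little more analysis work. If 12 schools is correct and some exclusions remain, either the stated power becomes slightly less favourable or the enrolment target rises. The change to the primary model needs no extra participants.

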The following five school districts in St. Louis County will be included: University City, Ferguson-Florissant, Normandy, Pattonville, and Jennings. Individuals who are students, staff, and household members of students and staff are eligible to participate in the various parts of the study. Sixteen middle and high schools from these school districts will participate. According to St. Louis County and regional hospital data, these districts are located in areas that have been most heavily impacted by COVID-19, especially in the early months of the pandemic. Additionally, all schools in this study receive Title 1 funding and have 100% of their students receiving free and reduced lunch. The percent of in-person attendance when available ranges from 20%-42%, and 18%-42% of families in these districts live below the poverty line.

D Study Procedures

D1 Testing Study Procedures

Recruitment and Consent

All research activities will occur among the students, parents/guardians, staff (teachers, aides, nurses, administrators) and household members of our participating school districts. All students (5-21 years old), school staff, and their household members (all ages) are eligible for inclusion in the study. Individuals will be excluded if they (or their parents/LAR) do not provide consent or are unable to provide saliva for testing.

Screening Testing Consent

Prior to starting screening testing, students, staff, and their household members will be consented or assented in-person (group or individual discussion), by phone, or by zoom. Middle and high school students under the age of 18 will provide assent (if cognitively able) for participation after we have obtained consent from their parent/LAR by phone, zoom or in person. Since household members/parents/LARs are not present in the school, they may receive a copy of the consent document prior to the consent discussion.

Symptomatic/Exposure Testing Consent

For symptomatic and/or exposure testing, we will obtain verbal consent and assent (when appropriate) prior to testing. A copy of the consent information will be provided. We will also have individuals sign an email communication form and note their email preferences. The email communication form might be in person or electronic since parents/LARs are not present at the school.

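### The stated 80% power for 12 schools needs equal school sizes and a reference distribution that ignores the number of schools; with 10 degrees of freedom it is 71.5%, and lower if sizes differ

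*Combined protocol and SAP*

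**What the plan says.** Section E, Power calculation, describes a cluster randomized trial in 12 schools: "Schools will be randomized 1:1 to either screening testing plus symptomatic testing, or symptomatic testing only". The inputs are these.

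- Effect: "We expect that transmission rates with screening testing or routine symptomatic testing will be 2% and 8%, respectively".
- Clustering: "the intracluster correlation coefficient (ICC) is 0.02".
- Spread: "the standard deviation of transmission rate is 0.22".
- Test: "using a two-sided t-test at a significance level of 0.05".
- Claim: "6 schools in each arm with an average of 117 participants per school will achieve 80% power". The words that matter here are "with an average of 117 participants per school".

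Table 3 varies the ICC and the SD and lists participants per school. It has no entry for variation in school size, and the text does not state the degrees of freedom of the t-test.

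Two statements elsewhere bear on this. Section C, Study Setting and Populations, notes: "The percent of in-person attendance when available ranges from 20%-42"%. That section and Section D1, Screening Testing, also give sixteen schools, eight of them allocated to screening, against the 12 in Sections A and E.

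**The concern.** The power sentence calls 117 an average, yet a calculation based on a single cluster size is exact only when all schools contribute equally. Nothing in the plan equalizes contributions: middle and high schools are mixed, participation is by consent, and attendance varies. Unequal clusters raise the design effect and lower power.

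The reference distribution matters more. With 12 randomized schools the treatment comparison has 12 − 2 = 10 degrees of freedom. A calculation that counts participants instead treats the between-school variance as almost perfectly known.

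If the power is overstated, a null result could be read as evidence that weekly screening adds nothing, when the trial had a materially larger chance of missing the planned difference than the stated 20%.

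**Working it through.** **Inputs.** From Section E: difference d = 0.08 − 0.02 = 0.06, SD = 0.22, ICC = 0.02, K = 6 schools per arm, m = 117, two-sided alpha 0.05. The CV of school contribution is not given and is an assumption throughout.

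**1. Reproduce the plan's figure, equal sizes.**

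- Design effect: DE = 1 + (m − 1)·ICC = 1 + 116 × 0.02 = 3.32.
- SE = SD·√(2·DE/(K·m)) = 0.22 × √(6.64/702) = 0.0214.
- d/SE = 2.804.
- Normal reference: Φ(2.804 − 1.960) = 80.1%.
- t with participant-level df, 2(K·m − 1) = 1,402: 80.0%. The smallest equal size reaching 80% is exactly 117.

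All ten rows of Table 3 give 80.0% to 80.2% this way. So the table assumes equal sizes and does not use school-level df. Whether the software used a normal reference or a t with participant-level df cannot be told apart from the results.

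**2. Change only the degrees of freedom.** With df = 2(K − 1) = 10 the critical value is 2.228. The noncentral t with noncentrality 2.804 gives **71.5%**. Sizes are still equal.

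**3. Add unequal sizes.** DE = 1 + ((1 + CV²)·m − 1)·ICC.

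To get a rough scale for CV, suppose only attendance varied, over 20% to 42% with midpoint 31%. A uniform spread gives (0.22/√12)/0.31 = 0.20. A two-point split at the ends gives 0.11/0.31 = 0.35. A CV of 0.5 stands for additional variation in enrollment, consent or case counts, and no figure in the documents supports it.

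| CV (assumed) | DE | 12 schools, plan's method (normal) | 12 schools, 10 df | 16 schools, 14 df |
|---|---|---|---|---|
| 0 | 3.320 | 80.1% | 71.5% | 85.3% |
| 0.20 | 3.414 | 79.0% | 70.3% | 84.3% |
| 0.35 | 3.607 | 76.7% | 68.0% | 82.3% |
| 0.50 | 3.905 | 73.4% | 64.5% | 79.3% |

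The last column keeps 117 per school and sets K = 8.

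**4. Efficient weighting, as a lower bound on the loss.** DE = 3.32/(1 − CV²·L·(1 − L)), with L = m·ICC/(m·ICC + 1 − ICC) = 2.34/3.32 = 0.705. For 12 schools at CV 0.20, 0.35 and 0.50, power is 79.7%, 79.1% and 77.9% by the plan's method, and 71.2%, 70.4% and 69.2% with 10 df.

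**5. Separate the two effects.** Degrees of freedom cost 80.1 − 71.5 = 8.6 points. Unequal sizes then cost 1.2 points at CV 0.20 and 3.5 points at CV 0.35 (1.1 and 3.4 by the plan's method, using the rounded figures above).

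**The case against.** A reader might infer that unequal school sizes alone sink the design, with power in the low seventies or sixties. The documents do not support that. By the plan's method power falls to 73.4% only at an assumed CV of 0.5, and to 64.4% at 0.8, and neither value has a source in the plan. The attendance range is the only documented variation, and it is a weak guide. It may describe districts rather than schools, it is a percentage of an unstated enrollment, and the outcome is defined per school-based case, so the relevant cluster size may be cases or contacts rather than participants.

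Nor does Table 3 contain an arithmetic error. Its rows reproduce, and planning on an average cluster size is a common simplification. The inputs it already varies can matter as much or more: at 117 per school, an SD of 0.23 gives 76.5% and an ICC of 0.03 gives 67.5% by the plan's method.

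The unequal-size formula in step 3 is also the pessimistic one, and efficient weighting would recover much of that loss. This stands in part. The plan specifies a GEE with a first-order autoregressive working correlation. If the fitted correlation is near 0.02 it dies out almost at once and weights participants nearly equally, which is closer to step 3 than to step 4.

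Finally, sixteen schools would put power above 80% at CVs of 0.20 and 0.35 even with 14 df. That stands. It confines the shortfall to the 12-school design, which is the one Section E makes its claim for.

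None of this answers the degrees-of-freedom point, which needs no assumption about school size.

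**Conclusion.** The concern holds in a limited form. The 80% claimed for 12 schools has no margin and depends on two conditions that the plan does not state: equal contributions and a reference distribution that ignores how few schools are randomized. Replacing the second gives 71.5% with the plan's own inputs. Dropping the first lowers it further, by about 1 to 3.5 points if the CV is 0.20 to 0.35 and by 7 points at 0.5. These CVs are assumptions, and the loss is smaller under efficient weighting. The direction is certain for any variation in size; the amount is not.

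The result takes the ICC, SD and difference as stated and treats 117 as the mean cluster size. It does not show that the trial as run is underpowered, because the documents disagree on whether 12 or 16 schools are randomized.

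**What to change.** 1. Reconcile 12 and 16 schools across Sections A, C, D and E, since this decides whether there is a shortfall.
2. Rerun the power calculation for that number with school-level degrees of freedom (number of schools minus 2), and state them.
3. Take the CV of school contribution from the districts' enrollment and case counts, and say whether the contributing unit is a participant, a contact or a case.
4. Replace the unconditional 80% claim with the resulting figure and its assumptions.
5. Add CV to Table 3 as a sensitivity range, for example 0, 0.20, 0.35 and 0.50.

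The cost is one rerun, a revised sentence and an added table column. It requires no additional schools. If 12 schools is correct, the stated power will be less favorable.

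### The GEE's first-order autoregressive working correlation needs a row order that the plan never defines and does not match the common ICC used for sizing; the cost is reproducibility and, if school sizes vary, some precision

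*Combined protocol and SAP*

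**What the plan says.** In Section E of the combined protocol and SAP, the Analysis plan proposes a GEE with an identity link for the primary outcome, because "the correlation among participants within each school needs to be considered". It then fixes the structure: "The autoregressive of first order as a working correlation structure will be used". Standard errors are to come from the sandwich estimator. The plan gives no ordering variable, spacing or sort key, no reason for the autoregressive choice, and no alternative structure.

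The Power calculation in the same section uses a different description of the correlation. It assumes that "the intracluster correlation coefficient (ICC) is 0.02 and the standard deviation of transmission rate is 0.22" and that "transmission rates with screening testing or routine symptomatic testing will be 2% and 8%, respectively". It concludes that "6 schools in each arm with an average of 117 participants per school will achieve 80% power", "using a two-sided t-test at a significance level of 0.05". Table 3 varies the ICC from 0.01 to 0.03, always as one value per row of the table. The outcome is defined as one ratio for each school-based case, not as repeated measurements on a person.

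**The concern.** A first-order autoregressive structure, AR(1), describes equally spaced sequential measurements: correlation falls geometrically with the distance between rows. Participants in a school have no first or last row, so the fitted correlation depends on how the file happens to be sorted. If the rows are cases, they do have dates. But the plan does not order by date, case dates are not equally spaced, and AR(1) would still treat early and late cases in one school as nearly unrelated, although a school effect persists.

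The sizing assumes the opposite: every pair in a school shares the same correlation. Two things are at stake. The analysis cannot be reproduced exactly from the plan, and if schools differ in size, the weights that AR(1) implies are not the efficient ones under the trial's own sizing model.

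**Working it through.** **Inputs.** From Section E: 6 schools per arm (k), average 117 participants per school (m), difference 0.08 − 0.02 = 0.06, SD 0.22, ICC 0.02, two-sided 0.05. Sections C and D1 give sixteen schools; I use the 12 of Section E, and the point does not depend on which is right. The coefficient of variation (CV) of school size is not in the documents; it is an assumption, shown from 0 to 0.8.

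**1. The plan's own figure.** With the exchangeable design effect:

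- DE = 1 + (117 − 1) × 0.02 = 3.32
- SE = 0.22 × √(2 × 3.32 / (6 × 117)) = 0.0214
- 0.06 / 0.0214 = 2.80, and Φ(2.80 − 1.96) = 0.80

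This reproduces 117 per school at 80% power. All ten rows of Table 3 reproduce within 1% in the same way, so the sizing does rest on a common ICC.

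**2. What AR(1) says instead.** With a lag-1 correlation of 0.02, correlation at lag 2 is 0.02² = 0.0004. The implied design effect is about (1 + 0.02)/(1 − 0.02) = 1.04. As a working structure this is almost independence.

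**3. Weights.** Under AR(1) with parameter r, interior rows get weight (1 − r)/(1 + r) and the two end rows 1/(1 + r), so a school's weight is nearly proportional to its size. Under exchangeability it is m/(1 + (m − 1) × ICC). Compare a school of 117 with one twice as large:

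- AR(1): ratio of weights about 2.
- Exchangeable: 117/3.32 = 35.2 against 234/(1 + 233 × 0.02) = 41.3, a ratio of 1.17.

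**4. Variance with the ICC known.** If every pair truly has ICC 0.02, the variance of an arm mean with row weights w is proportional to Σ_j[(1 − ICC)Σ_i w² + ICC(Σ_i w)²] / (Σ_jΣ_i w)². Averaged over gamma-distributed school sizes with mean 117:

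| Assumed size CV | Efficiency of AR(1) relative to exchangeable | Variance increase (1/efficiency − 1) |
|---|---|---|
| 0 | 1.000 | 0% |
| 0.3 | 0.967 | 3% |
| 0.5 | 0.922 | 8% |
| 0.65 | 0.887 | 13% |
| 0.8 | 0.857 | 17% |

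Independence weights give the same efficiencies to three decimals at CVs from 0.3 to 0.8. A separate calculation of size-weighted against optimally weighted arm differences gave +6%, +13% and +18% at CV 0.4, 0.65 and 0.8. The corresponding normal-approximation power is 76% against 79%, 71% against 76%, and 67% against 74%.

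**5. Correlation estimated from the data.** In simulated GEE fits with 12 schools and the arm term only:

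- Equal schools: the SD of the effect was 0.0214 under both structures.
- CV 0.5: 0.0225 (AR(1)) against 0.0216, a variance ratio of (0.0225/0.0216)² = 1.09. Power was 82.3% against 82.7%.
- CV 0.8: 0.0254 against 0.0236, a variance ratio of (0.0254/0.0236)² = 1.16. Power was 79.2% against 80.6%.
- Binary outcomes, AR(1) actually fitted: variance loss 2-4%.
- Binary outcomes, size-weighting standing in for AR(1): 6%, 11% and 13% at CV 0.4, 0.65 and 0.8.

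The simulated powers use an uncorrected z reference that over-rejects under the null, so only the differences between structures are informative.

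**6. Row order.** Sixty random re-sorts within schools, in each of 180 simulated data sets, moved the fitted AR(1) parameter from about −0.05 to +0.08. The arm effect moved by about 2% of its SE on average (largest 5%), and significance changed in none of the 180. In another simulation the parameter was 0.14 sorted by case and 0.02 shuffled, while the arm effect moved by about 1% of its SE. An extreme order, sorting by the outcome, drove the parameter to 0.94 in one data set, moved the estimate from −0.102 to −0.112 and the SE from 0.017 to 0.025.

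**The case against.** In a GEE with sandwich errors, the working correlation is a weighting device, not a claim about the truth. The within-school correlation enters the standard error empirically, so AR(1) does not deny the ICC in the inference. That stands.

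A reader might infer from the design effects of 3.32 and 1.04 that standard errors would be about √(3.32/1.04) = 1.8 times too small. The documents do not support this: it describes a model-based SE, and the plan specifies the sandwich. Nor do they support reading the 3- to 7-point power gaps in step 4 as the expected gain. Those need the ICC to be known and the assumed size variation to be true; the simulated differences were 0.4 and 1.4 points.

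It is also fair that cases accrue over several quarters, so correlation that decays with time is plausible, and a stated sort key alone would restore reproducibility. But the plan states neither an order nor that rationale.

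The strongest point is that exchangeable weights have a cost. They give large schools relatively less weight, so if transmission depends on school size, the estimated quantity changes. In one simulation with the rate assumed to rise with size (CV 0.65), the expected effect was −0.071 size-weighted, −0.063 exchangeable and −0.060 with schools weighted equally. Section D1 defines the outcome as an average per case at each school, so the weighting deserves a deliberate choice.

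**Conclusion.** The concern holds as a specification defect of modest size. AR(1) has no defined order here and does not match the correlation model behind the sample size. Inference remains asymptotically valid, so there is no bias or Type I error problem attributable to this choice. Realistic changes of row order barely move the arm effect.

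The precision loss is conditional. It is nil with equal schools and about 3-18% of variance for assumed size CVs of 0.3-0.8 with the true ICC known to be 0.02. It is smaller when the correlation is estimated from binary data: 2-4% in one simulation, though up to 13% in another that used size-weighting as a proxy. The plan gives only an average school size, so the documents do not settle where in this range the trial falls.

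The small number of clusters is a separate matter. With 12 schools, the uncorrected sandwich z-test rejected 10-13% of the time under the null whichever working correlation was used. Changing the structure does not cure that.

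**What to change.** In the Analysis plan, replace the first-order autoregressive structure with an exchangeable one, with school as the cluster. Keep the sandwich standard errors and report the estimated ICC beside the planned 0.02. Add an independence-weighted sensitivity analysis, so that any dependence of the result on school size is visible.

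If serial correlation between cases is really intended, say so, state the ordering variable and how unequal spacing is handled, and keep the exchangeable fit as a sensitivity analysis.

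The cost is one phrase in the plan and one extra model fit. The small downside is the shift in weighting described above, which the sensitivity analysis is there to show. A small-sample correction for 12 clusters needs its own decision.
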